### *E.3. Subgroup analyses*

To examine heterogenous effects of the cash benefits, we will repeat our analyses for four pre-specified subgroups, each defined based on data from the pre-randomization period. The subgroups are: (1) chronic disease at baseline, (2) financial distress at baseline, and (3) poor self-reported health at baseline, or (4) any of the prior.

Specifically, we use electronic health record data to define participants by whether they have a known chronic disease (e.g., diabetes, hypertension, depression, anxiety). For a subset of the participants, we have baseline survey data that enables subgroup analyses by level of financial distress and self-reported health. Financial distress is defined as an affirmative answer on a survey question asking the participant whether she/he/they had any bills, expenses, or needs that they were unable to pay. Poor self-reported health is defined as a positive screening (score $\geq$ 3) on the 2-question version of the Patient Health Questionnaire, a positive screening (score $\geq$ 3) on the 2-question version of the Generalized Anxiety Disorder questionnaire, or a fair/poor response on the 5-point scale of self-rated health.

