### *E.2. Statistical specification*

Our primary analytic approach is an analysis based on the intent-to-treat principle that compares outcomes for those randomized into the treatment group to those who were randomized into the control group. Specifically, we will estimate the following linear regression model:

$$y_i = \beta_0 + \beta_1 \text{CASH}_i + \beta_3 \mathbf{X}_i + \epsilon_i,$$

where  $y_i$  is the utilization or clinical outcome for individual or household  $i$ . See section D.2. for a list of our primary and secondary outcomes. “ $\text{CASH}_i$ ” is an indicator for whether individual  $i$  won the lottery and was thus randomized into the treatment group.  $\mathbf{X}_i$  is a vector of covariates, specifically patient characteristics, including baseline (pre-randomization) values of the outcome variable, which are not explicitly necessary since they should be unrelated to treatment status, but they may increase the precision of our estimates to the extent that they explain some of the variance in the outcome.

The coefficient on  $\text{CASH}_i$ ,  $\beta_1$ , is our main coefficient of interest; it provides the difference in means between the treatment groups and the control group. In addition to our primary specification above that corresponds to testing for a level shift, we will also include an interaction term between an indicator for time and treatment status to test for changes in slope.

As described in section C, a household could receive additional lottery tickets by meeting specific criteria. Observations will thus be weighted by the inverse probability of winning the lottery so that  $\beta_1$  is an unbiased estimate of the relationship between winning the lottery and the outcome. An alternative specification that includes indicators for number of lottery tickets is discussed below. Standard errors will be clustered at the household level and adjusted for heteroskedasticity.

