#### *E.4. Alternative specifications and sensitivity analyses*

Our primary specification includes patient characteristics and baseline values of the outcome in the model to improve power as well as any chance imbalance between the study arms after randomization. As described in section E.1., we will compare covariates between the treatment and control groups, and we will explore whether our results are sensitive to inclusion of these covariates in the model. Importantly, our primary specification accounts for differential probability of winning the lottery using inverse probability weights. As an alternative approach, we will include the set of covariates that are correlated with treatment probability into the model, specifically indicators for number of lottery tickets. Finally, as a sensitivity check, we will also conduct our analyses on the subpopulation of participants with established primary care at one of the clinical sites of care.

To ensure our estimates are robust to method of estimation, we will also estimate generalized linear models assuming a negative binomial distribution for the count utilization outcomes and a generalized linear model with a Bournoulli distribution and logit link function for the binary outcomes. In a final robustness check, we will Winsorize the utilization measures to ensure that our estimates are not sensitive to outliers.

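### E.3 sets out to examine heterogeneous effects but only repeats the E.2 model within subgroups; no CASH-by-subgroup contrast is planned, so the method cannot show whether effects differ

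*Combined protocol and SAP*

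**What the plan says.** E.3 gives the aim and the method in one sentence: "To examine heterogenous effects of the cash benefits, we will repeat our analyses for four pre-specified subgroups". The groups are "each defined based on data from the pre-randomization period", which is a real safeguard. The first three are chronic disease, financial distress and poor self-reported health; the fourth is their union, "or (4) any of the prior".

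The data sources differ. For chronic disease, "we use electronic health record data to define participants by whether they have a known chronic disease". For the other two factors, "For a subset of the participants, we have baseline survey data that enables subgroup analyses by level of financial distress and self-reported health". The size of the surveyed subset is not stated.

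The model to be repeated is in E.2. Its coefficient of interest, β₁, is the treatment-control difference in means in whatever sample is analysed. E.2 contains one interaction: "we will also include an interaction term between an indicator for time and treatment status to test for changes in slope". E.4 adds analyses that vary the covariates, handling of lottery tickets, model family, outliers and the primary-care restriction. E.5 sets a threshold for the primary outcome and adjusts across secondary outcomes. Neither E.4 nor E.5 mentions subgroups.

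**The concern.** A statement about heterogeneity is a statement about a difference between two effects. The planned method yields one effect per subgroup. The authors do specify an interaction where they want to test for a change in slope over time, but none for the question posed in E.3.

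At stake is how the subgroup results are read. If the effect is the same in all women, chance and unequal subgroup sizes will often make one group significant and another not. Without a planned contrast, and with no statement that the subgroup results are exploratory or how they should be interpreted, such a pattern could be reported as a differential effect. The plan would then contain no prespecified quantity to support or refute that claim.

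**Working it through.** **Reading the plan.** Set side by side, E.3 asks about variation in effect; E.2 supplies β₁ within a sample; the E.2 interaction concerns time; E.4 and E.5 add no comparison between subgroups. The wording in E.3 about defining women by whether they have a chronic disease, and by level of distress and self-reported health, may mean that complements are analysed too. Two separate estimates still do not include an estimate or interval for their difference.

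**Illustration.** The documents state no power, effect size, subgroup size or survey share, so there is no plan figure to reproduce. Assumptions: one common true effect, equal variances, weights and clustering ignored, subgroup and complement independent, each tested at two-sided 0.05.

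Let s be the subgroup's share of the sample and δ the expected z-score of the overall effect, found from Φ(δ − 1.96) + Φ(−δ − 1.96) = overall power. The subgroup has expected z-score δ√s and power a; the complement has δ√(1 − s) and power b. The chance that exactly one is significant is a(1 − b) + b(1 − a).

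| Overall power | δ | s = 0.2: a, b | Exactly one | s = 0.5: a = b | Exactly one |
|---|---|---|---|---|---|
| no effect | 0 | 0.050, 0.050 | 0.095 | 0.050 | 0.095 |
| 50% | 1.960 | 0.142, 0.418 | 0.441 | 0.283 | 0.406 |
| 80% | 2.802 | 0.240, 0.707 | 0.608 | 0.508 | 0.500 |
| 90% | 3.242 | 0.305, 0.826 | 0.627 | 0.630 | 0.466 |

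For example, at 80% power and s = 0.2: 0.240 × 0.293 + 0.707 × 0.760 = 0.070 + 0.537, or about 0.608. A share of 0.8 gives the same result as 0.2 with the roles exchanged. Across 50-90% power the range is 0.406 to 0.627. At 20% overall power (δ = 1.115) it is about 0.22.

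**Precision of the proper contrast.** If the overall estimate has variance V, the two strata have variances V/s and V/(1 − s), so their difference has variance V/[s(1 − s)]. The ratio of standard errors is 1/√[s(1 − s)]: 1/√0.25 = 2.0 at s = 0.5 and 1/√0.16 = 2.5 at s = 0.2. The comparison is with the overall effect in the same sample. For the two survey-based factors that sample is the respondents, so relative to the full sample the ratio rises by a further 1/√f for a surveyed share f.

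**Power of the contrast.** For a true difference as large as the overall effect, the expected z-score is δ√[s(1 − s)]. Power for s from 0.2 to 0.5 is 7-9% at 20% overall power, 12-17% at 50%, 20-29% at 80% and 25-37% at 90%.

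**The case against.** The strongest reply is that E.3 promises only to examine heterogeneity. It does not say that significance in one group will be set against non-significance in another, and the 0.05 threshold in E.5 is tied to the primary outcome. A reader might infer that the plan intends to declare effects different from separate p-values; the text does not say so. The 41-63% therefore describes what happens if results are read that way and is not a measured error rate of this plan. That part of the objection stands.

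It can also be said that if complements are reported, anyone can subtract the two estimates. This is partly right: most of the information would be there. But the plan does not commit to reporting complements or to the subtraction, and members of one household may fall in different strata, so a standard error that ignores shared households is only approximate.

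A reader might also infer that group 4 is misclassified as planned. The documents do not support this. An unsurveyed woman with recorded chronic disease belongs in group 4 by definition. An unsurveyed woman without it has two of the three criteria unknown, but that matters only if group 4 is contrasted with other women, and E.3 never names such a complement.

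Finally, the contrasts will have low power. That is true, and it is a reason to show the interval and limit claims. It does not make separate subgroup estimates evidence of a difference.

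**Conclusion.** The gap is real: the method stated in E.3 cannot show whether the effect of the cash benefit differs between groups. It reaches no further than that. A reader might infer bias in the primary comparison or in the subgroup estimates; nothing here supports that, since the groups are prespecified and defined before randomization. What is affected is any claim of differential effects.

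The absence of a contrast follows from the text and does not depend on the illustration. The 41-63% rests on a common effect, 50-90% overall power, subgroup shares of 20-80%, equal variances, and no allowance for weights or clustering. None of these inputs comes from the documents, and at lower power the figure is smaller. The plan should be changed, but this is a matter of secondary interpretation.

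**What to change.** In E.3, for each of the first three factors, fit the E.2 model with the subgroup indicator, CASH×subgroup and X×subgroup, using the same inverse-probability weights and household-clustered standard errors. Use all matched women for chronic disease, and survey respondents for financial distress and poor self-reported health. The X×subgroup terms are needed: with common covariate coefficients, the interaction would not in general equal the difference between the subgroup and complement estimates printed beside it.

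Report both stratum estimates and their difference with a confidence interval. State that any heterogeneity claim rests on that difference, and label it exploratory.

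For group 4, keep the within-group estimate as defined, including unsurveyed women with recorded chronic disease. If group 4 is contrasted with other women, do so among surveyed women only, so that both sides are classified on the same information, and say that this contrast covers a different set of women from the within-group estimate.

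The cost is a few sentences in the SAP and a few model lines, with no new data. The downside is imprecision, as shown in the working: the benefit is mainly an interval and a limit on what is claimed, with little prospect of detecting a modest difference.

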#### *E.4. Alternative specifications and sensitivity analyses*

Our primary specification includes patient characteristics and baseline values of the outcome in the model to improve power as well as any chance imbalance between the study arms after randomization. As described in section E.1., we will compare covariates between the treatment and control groups, and we will explore whether our results are sensitive to inclusion of these covariates in the model. Importantly, our primary specification accounts for differential probability of winning the lottery using inverse probability weights. As an alternative approach, we will include the set of covariates that are correlated with treatment probability into the model, specifically indicators for number of lottery tickets. Finally, as a sensitivity check, we will also conduct our analyses on the subpopulation of participants with established primary care at one of the clinical sites of care.

To ensure our estimates are robust to method of estimation, we will also estimate generalized linear models assuming a negative binomial distribution for the count utilization outcomes and a generalized linear model with a Bournoulli distribution and logit link function for the binary outcomes. In a final robustness check, we will Winsorize the utilization measures to ensure that our estimates are not sensitive to outliers.

#### *E.5. Statistical significance and adjustments for multiple comparisons*

Statistical significance was defined as two-sided  $P < 0.05$  for the primary outcome. Because we have one prespecified primary outcome, we will not make any adjustments for multiple inference. For our secondary outcomes, we will use the Benjamini-Hochberg procedure or similar to calculate adjusted p-values that account for testing of multiple outcomes.
